3.1 Study Rationale

JUVÉDERM VOLITE without lidocaine was CE-marked in 2015, and the product with lidocaine was CE-marked in 2016. An open-label European study (V12-001) of JUVÉDERM VOLITE without lidocaine provided evidence of the product's safety and effectiveness in improving facial skin smoothness, and it serves as a feasibility study. This protocol is designed as a pivotal study to collect safety and effectiveness data on JUVÉDERM VOLITE XC for improvement in facial skin smoothness in order to support FDA product approval.

3.2 Background

JUVÉDERM VOLITE XC (HA concentration 12 mg/mL) is the newest member of the VYCROSS® technology platform, which includes JUVÉDERM VOLBELLA® XC (15 mg/mL, FDA-approved in 2016), JUVÉDERM VOLLURE™ XC (17.5 mg/mL, FDA-approved in 2017), and JUVÉDERM VOLYUMA® XC (20 mg/mL, FDA-approved in 2013). Each VYCROSS product is specifically tailored for its relative clinical use (lift capacity and spreadability), with JUVÉDERM VOLITE XC having the lowest HA concentration to serve the unmet need of a filler for fine lines. JUVÉDERM VOLITE XC also contains 0.3% lidocaine (w/w gel) to reduce injection pain and uncrosslinked HA to ease filler extrusion, which is the same amount of lidocaine and uncrosslinked HA included in VOLBELLA and VOLYURE.

The safety of JUVÉDERM VOLITE XC is supported by preclinical biocompatibility data, which show that it is nontoxic, noncytotoxic, nongenotoxic, nonirritant, nonsensitizing, noncarcinogenic, and nonpyrogenic.

A prospective, single-arm European postapproval study (V12-001) was conducted at a single center (6 injecting physicians from 6 countries) to assess the safety and effectiveness of JUVÉDERM VOLITE without lidocaine in treating fine lines and skin roughness in the face and neck. Treatment was administered on both sides of the face (cheek and forehead) and neck (if desired) for fine lines and the improvement in skin roughness. For 131 treated subjects, a total of 261 cheeks, 120 foreheads, and 96 necks were treated. Touch-up treatments were provided for 31 subjects (23.7%) and 46 cheeks (17.6%), and repeat treatments at 9 months were provided for 62 subjects (47.3%) and 124 cheeks (47.5%). The responder rate on the ACSS (formerly known as the Allergan Skin Roughness Scale) was 96.2% at Month 1, 76.3% at Month 4, 34.9% at Month 6, 15.8% at Month 9, and 87.1% at 1 month after repeat treatment. Among treated cheeks with scores of moderate or severe at baseline on the ACSS, the ACSS responder rate was 89.4% at Month 1, 66.7% at Month 4, 40.5% at Month 6, 15.6% at Month 9, and 94.3% at 1 month after repeat treatment. A statistically significant improvement ($p < 0.001$) in subject satisfaction with

skin based on the FACE-Q Satisfaction with Skin questionnaire was observed at all timepoints. The V12-001 study served as the basis for the present study's sample size calculations (see [Section 10.1](#)) and injection volumes and treatment characteristics (see [Section 5.5](#)) as well as a study follow-up duration of 6 months based on the product's observed clinical duration.

3.3 Device Description

JUVÉDERM VOLITE XC is a sterile, biodegradable, nonpyrogenic, viscoelastic, clear, colorless, homogeneous, HA gel implant (dermal filler). It consists of crosslinked HA produced by the *Streptococcus* species of bacteria, formulated to a concentration of 12 mg/mL and 0.3% lidocaine in a physiological buffer. The gel is provided in a plastic syringe, which is packaged with two 32 G 1/2" needles, and 32 G 3/16" needles are provided separately.

3.4 Benefit/Risk Assessment

A risk analysis linked to the manufacturing, biocompatibility, and usage of JUVÉDERM VOLITE XC was conducted according to ISO 14971:2007/EN ISO 14971:2012 and is detailed in the risk management file.

The injection procedure, anesthetic agents, or JUVÉDERM VOLITE XC may cause some of the risks and/or discomforts listed below. Unforeseeable risks or results are also a possibility. The risk of developing a serious complication is small. If a complication occurs, subjects will be advised to contact the TI who will use his/her medical judgment to do whatever is necessary to treat the subject.

As with any skin injection, risks can be posed by the injection procedure itself, the anesthetic agent, and injection of JUVÉDERM VOLITE XC injectable gel. Risks related to the injection procedure include redness, itching, pain, tenderness, swelling, bruising, and lumps and bumps, which are common to dermal filler injection procedures in general. The use of a small gauge needle to deliver JUVÉDERM VOLITE XC used in this study is intended to minimize tissue trauma. The inclusion of 0.3% lidocaine in the formulation is meant to reduce pain during the injection, and this needs to be taken into account when administering concomitant additional anesthetics as well as in relation to subjects' medical history (ie, allergy to lidocaine). Risks associated with the anesthetic agent include allergic reactions that may manifest as an anaphylactic reaction, skin rash, redness, itching, hives, burning, stinging, swelling, tenderness, and transient loss of skin color.

Prior to administering any topical pretreatment anesthesia, the TI will thoroughly review the subject's history to confirm the suitability of the planned anesthetic agent. Additionally, the investigational DFU must be carefully reviewed, and each individual subject's medical history must be carefully considered, when evaluating a potential subject's candidacy for study enrollment.

The benefit of using HA dermal fillers in facial aesthetics has been documented in the published literature showing the safety and effectiveness of HA dermal fillers. It is anticipated that the safety and effectiveness of treatment to improve facial skin smoothness are similar to those identified in studies of JUVÉDERM products for equivalent indications such as perioral lines. The physicochemical properties of JUVÉDERM VOLITE XC potentially provide the benefit of use of HA dermal fillers for improvement in facial skin smoothness.

More detailed information about the known and expected benefits and risks and reasonably expected AEs of JUVÉDERM VOLITE XC are provided in the investigational DFU.

4. Objectives and Endpoints

4.1 Study Objectives and Endpoints

The objective of this study is to evaluate the safety and effectiveness of JUVÉDERM VOLITE XC in subjects seeking improvement in cheek skin smoothness.

Objectives	Endpoints/Measures
Effectiveness To evaluate the effectiveness of JUVÉDERM VOLITE XC in adult subjects seeking improvement in cheek skin smoothness	
 Primary: ACSS responder status at Month 1 Secondary: Change from baseline to Month 1 on FACE-Q Satisfaction with Skin questionnaire Secondary: AFLS responder status at Month 1 Other: Primary and secondary endpoints at other applicable timepoints Other: Change from baseline on FACE-Q Appraisal of Lines Overall questionnaire Other: Natural look and feel of the skin Other: Global aesthetic improvement on GAIS Other: Change from baseline in cheek skin hydration measured by MoistureMeter® D instrument Exploratory: Composite responder status on ACSS and FACE-Q Satisfaction with Skin questionnaire
Safety To evaluate the safety of JUVÉDERM VOLITE XC in adult subjects seeking improvement in cheek skin smoothness	
 FACE-Q Recovery Early Life Impact questionnaire Procedural pain ISRs AEs Snellen visual acuity, confrontational visual fields, ocular motility

4.2 Clinical Hypotheses

The clinical hypothesis is that the percentage of subjects with a clinically significant change (defined as at least a 1-point improvement on the ACSS as assessed by the EI) in cheek skin smoothness from baseline to Month 1 for both cheeks will be significantly greater in the JUVÉDERM VOLITE XC treatment group than in the untreated control group.

5. Study Design

5.1 Overall Design

[figure not shown]
This is a multicenter, evaluator-blind, controlled, parallel-design, prospective study of adults seeking improvement in cheek skin smoothness. Up to 20 investigational sites will enroll and follow subjects who meet the study criteria according to the study design in [Figure 5-1](#). Each site will have a PI who is responsible for the overall conduct of the study at that site and may also be the TI. The TI performs all study treatments, and the blinded EI evaluates ACSS, AFLS, and skin hydration measurements.

The study will span a total of approximately 20 months: an estimated 9 months for recruitment and 11 months for follow-up. For the treatment group, each subject's participation will encompass up to 30 days of treatment and up to 10 months of follow-up (6 months for those choosing not to receive repeat treatment at Month 6). For the control group, each subject's participation will encompass 1 month; for control subjects who opt to receive treatment, the treatment period will be up to 30 days, and the follow-up period will be up to 6 months.

Treatment group subjects receive initial treatment and optional touch-up treatment at 30 days if needed to achieve optimal correction. Follow-up visits are 3 days after each treatment (safety only) and at Months 1, 2, 4, and 6 after last treatment. Subjects exit the study at Month 6 or receive repeat treatment and are followed at Day 3 and Months 1 and 4 after repeat treatment. Control group subjects are followed for 1 month after randomization (no-treatment control period) and then either exit the study or receive optional treatment (initial and touch-up, if needed) in the delayed treatment period. Post-treatment follow-up visits are 3 days after each treatment and at Months 1, 2, 4, and 6 after last treatment.

To ensure adequate enrollment of subjects with Fitzpatrick skin phototype V and VI, up to 10 subjects may be enrolled in the Fitzpatrick V/VI safety cohort with less stringent inclusion criteria (see [Section 6.1](#)) and followed for safety only.

Figure 5-1 Study Design

5.2 Subject and Study Completion

A maximum of 263 subjects will be enrolled at up to 20 US sites in order to have 210 subjects randomized and 112 treatment group subjects and 56 control group subjects complete the study based on an anticipated dropout rate of 20%. A maximum of 20% of the study population may be enrolled at any 1 investigational site. See [Section 10.1](#) for explanation of sample size determination.

5.3 End of Study Definition

The end of the study is defined as the date of the last visit of the last subject in the study.

A subject is considered to have completed the study if he/she has completed all phases of the study including the last visit. Treatment group subjects who elect not to receive repeat treatment are considered completers if they complete the Month 6 visit. Control group subjects who elect not to receive treatment are considered completers if they complete the Month 1 visit.

5.4 Scientific Rationale for Study Design

This pivotal study was designed with a no-treatment control because there are no FDA-approved dermal fillers for improving cheek skin smoothness to use as a comparator.

5.5 Justification for Device Volume and/or Treatment Administration

In the V12-001 study of JUVÉDERM VOLITE, subjects could receive up to 7 mL in the face and neck. Within this limitation, the maximum volume injected in the cheeks was 2.5 mL total at

initial treatment and 2 mL at touch-up treatment. To ensure that optimal correction can be obtained, the maximum allowable injection volume for this study in the cheeks was set at 4 mL for initial treatment and 2 mL for touch-up treatment. An additional 4 mL is allowed for repeat treatment at Month 1. Consistent with the product attributes and V1 2-001 study methods, treatment is to be performed in multiple microdepot intradermal injections via 32 G 1/2" or 32 G 3/16" needles, as described in the investigational I FU provided in the Site Study Binder.

6. Study Population

Adults seeking improvement in cheek skin smoothness. The randomization target is a minimum of 20 subjects of Fitzpatrick skin prototypes I/II, 20 of prototypes III/IV, and 20 of prototypes V/VI (up to 10 of whom may be enrolled in the Fitzpatrick V/VI safety cohort).

Prospective approval of protocol deviations to recruitment and enrollment criteria, also known as protocol waivers or exemptions, is not permitted.

6.1 Inclusion Criteria

Subjects are eligible to be included in the study only if all of the following criteria apply:

1. Age 22 or over and in good general health
2. Has an ACSS score of 2 for both cheeks or 3 for both cheeks on the 5-point Allergan Cheek Smoothness photonumeric scale (range: 0 to 4), as judged live by the Evaluator (Fitzpatrick V/VI safety cohort)
3. Has a FACE-Q Satisfaction with Skin Questionnaire sum score of 39 or less (sum score of 39 is equivalent to Rasch-transformed score of 69) unless enrolled as part of the Fitzpatrick V/VI safety cohort
4. Ability to follow study instructions and likely to complete all required visits
5. Written informed consent and data privacy consent have been obtained

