10.3.1.2 Primary Endpoint Analysis

The primary effectiveness variable is the EI's assessment of cheek skin smoothness on the ACSS. The primary effectiveness analysis is the ACSS responder rate at Month 1. A responder is defined as a subject who shows at least a 1-point improvement from baseline on the ACSS scale on both cheeks. The responder rate and corresponding 95% confidence interval will be summarized. A 2-sided, Fisher's exact test at the 5% level will be used to test whether the ACSS responder rate at Month 1 in the treatment group is significantly greater than that in the control group at Month 1 in the control period.

The primary effectiveness analysis will test for superiority of JUVÉDERM VOLITE XC treatment group over no treatment in the difference in ACSS responder rate based on the EI's assessment at Month 1. Month 1 refers to 1 month after the last treatment (initial or touch-up) for subjects in the JUVÉDERM VOLITE XC treatment group and 1 month after randomization for subjects in the no-treatment control group.

The null hypothesis is that the responder rate for the JUVÉDERM VOLITE XC treatment group is equal to the responder rate for the no-treatment control group. The alternative hypothesis is that the responder rates are not equal for the treatment group and the no-treatment control group. These hypotheses are stated as:

$$H_0: P_v - P_c = 0$$
$$H_a: P_v - P_c > 0 \text{ or } P_v - P_c < 0$$

where Pv and Pc denote the responder rates for the JUVÉDERM VOLITE XC group at Month 1 after last treatment (initial or touch-up) and for the no-treatment control group at Month 1 after randomization, respectively. Two-sided Fisher's exact test with 5% significance level will be used to compare treatment effects between JUVÉDERM VOLITE XC and the no-treatment control group. If the 2-sided p-value is less than 0.05 and the responder rate is greater for JUVÉDERM VOLITE XC than for the no-treatment control group, then JUVÉDERM VOLITE XC will be considered superior to the no-treatment control group.

For primary analysis, subjects with missing data at the primary timepoint (ie, Month 1) will be analyzed as non-responders. Details will be described in the SAP.

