The primary effectiveness variable is the cheek skin smoothness based on the ACSS evaluated by EIs. The primary effectiveness endpoint is the ACSS responders at Month 1 defined as a participant who achieves at least a 1-point improvement from baseline on both cheeks based on ACSS. Month 1 refers to 1 month after the preceding treatment (initial or touch-up) for participants in the JUVÉDERM VOLITE XC treatment group or 1 month after randomization for participants in the no-treatment control group.

The null hypothesis is that there is no difference between the JUVÉDERM VOLITE XC treatment group and the no-treatment control group in the ACSS responder rate at Month 1. The alternative hypothesis is that there is difference between the JUVÉDERM VOLITE XC treatment group and the no-treatment control group in the ACSS responder rate at Month 1. These hypotheses are stated as:

$$H_0: P_v - P_c = 0$$

$$H_a: P_v - P_c > 0 \text{ or } P_v - P_c < 0$$

where P_v and P_c denote the responder rates for the JUVÉDERM VOLITE XC group at Month 1 after the preceding treatment (initial or touch-up) and for the no-treatment control group at Month 1 after randomization, respectively. The treatment effects between JUVÉDERM VOLITE XC and the no-treatment control group will be compared using the statistical method described in [Section 5.3.2](#). If the 2-sided p-value is less than 0.05 and the responder rate is greater for JUVÉDERM VOLITE XC than for the no-treatment control group, then JUVÉDERM VOLITE XC will be considered superior to the no-treatment control group.

3. Sample Size Determination

A sample size of 112 participants in the treatment group and 56 participants in the control group will provide 99.9% power to detect a difference of at least 40% in the responder rates on the ACSS between the groups, based on a 2-sided Fisher's exact test at the 5% level. The treatment group is assumed to have at least an 80% responder rate at Month 1, and the control group is assumed to have at most a 40% responder rate. The assumptions of responder rates are estimated from Allergan Study V12-001. Accounting for participant attrition of 20% during the study, 210 participants will be randomized at a 2:1 ratio to treatment group and control group. Randomization will occur within each study site.

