5.3.2. Main Analytical Approach

The missing data in ACSS at Month 1 of CP will be imputed using the Multiple Imputation (MI) method for the mITT population as follows:

Step 1: The missing data will be imputed by cheek side and treatment group using the Fully Conditional Specification (FCS) method with seed = 820403 and nimpute = 30 based on the following model:

$$\text{Month 1 ACSS} = \beta_0 + \beta_1 \times \text{Age} + \beta_2 \times \text{Baseline ACSS}$$

Step 2: After imputation, the changes from baseline will be calculated, from which the responder status in ACSS at Month 1 of CP will be determined.

Step 3: Each complete dataset obtained from Steps 1 and 2 will be analyzed using SAS procedure FREQ

Step 4: The pooled results will be obtained using PROC MIANALYZE

The number and proportion of participants who achieved at least 1-point improvement from baseline at Month 1 of CP will be tabulated by treatment group. The aggregated responder rates by treatment group and the associated p-value and 95% CI estimated based on the normal approximation to assess the difference in the ACSS responder rate at Month 1 of CP between JUVÉDERM VOLITE XC and the no-treatment control will be presented. If the 2-sided p-value is less than 0.05, then the ACSS responder rate at Month 1 in JUVÉDERM VOLITE XC is statistically significantly different from that in the no-treatment control group during the control period. Furthermore, if the responder rate is greater for JUVÉDERM VOLITE XC than the no-treatment control group, then VOLITE will be considered superior to the no-treatment control group.

The detailed SAS codes are as follows:

```
proc mi data=adeff seed=820403 nimpute=30 out=mi;
  by trt01p cheek;
  class acss0 acss1;
  fcs logistic(/details);
  var age acss0 acss1;
run;
data lmi rmi; *separate imputed datasets by cheek side;
  set mi;
  if cheek='Left' then output lmi;
  if cheek='Right' then output rmi;
run;
data all; *obtain responder status variable;
  merge lmi rmi;
```

JUVÉDERM VOLITE™ XC

```
by _imputation_ subjid;
ldiff=lacss0-lacss1;
rdiff=racss0-racss1;
resp=0;
if ldiff >= 1 and rdiff>=1 then resp=1;
run;
ods output RiskDiffCol2=risk(where=(index(row,'Total')=0));
proc freq data=all;
  by _imputation_;
  tables trt01p*resp/riskdiff;
run;
proc sort data=risk; by row;
ods output VarianceInfo=Variance1;
ods output ParameterEstimates=Param1;
proc mianalyze data=risk;
  by row;
  modeleffects risk;
  stderr ase;
run;
```

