5.4.2. Main Analytical Approach

For the secondary effectiveness endpoint of change from baseline in FACE-Q Satisfaction with Skin overall converted score at Month 1, a 2-sided 2-sample t-test, if the normality assumption holds, otherwise, the Wilcoxon rank-sum test will be used to compare mean change from baseline values between treatment and control groups using the mITT population.

For the secondary effectiveness endpoint of AFLS responder status at Month 1, the 95% CI will be provided for the proportion of responders for each treatment group. For comparison of treatment group versus control group at Month 1, the responder rate difference, 95% CI for the risk difference and p-value will be estimated based on Fisher's exact test using the mITT population with baseline AFLS score of 2 on both cheeks or 3 on both cheeks.

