5.7. Other Analyses

5.7.1. Subgroup Analyses

Analysis of the primary effectiveness endpoint, ACSS responder status at Month 1, will be performed separately by the following subgroups based on the observed data:

- Baseline ACSS score: 2 and 3
- Fitzpatrick skin phototype: I/II, III/IV, and V/VI

JUVÉDERM VOLITE™ XC

- Volume injected: \leq median and $>$ median
- Injection plane/technique: microdepot intradermal injection vs. other injections
- Investigational site

The median total volume injected for the initial and touch-up treatments combined on both cheeks will be calculated to determine the cut-off for the subgroup listed above. Participants who received microdepot non-intradermal injections, non-microdepot intradermal, or non-microdepot non-intradermal injections for the initial or touch-up treatment are included in the subgroup of “other” injections.

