6.2. Appendix 2: Changes to SAP Version 1 Analyses

The following are changes to [version 1](#) of SAP:

1. The naming of the analysis population for the sensitivity analysis of primary endpoint, ACSS responder status at Month 1 was changed from “Completer Population” to “Observed Primary Endpoint” in Section 4. The definition of this population refers to the completion of the primary timepoint visit (ie., Month 1 of CP). This naming change is aimed to avoid potential confusion with study completion.
2. The wordings of “overall converted score” were specified for the analyses of FACE-Q Satisfaction with Skin, FACE-Q Appraisal of Lines, and FACE-Q Recovery Early Life Impact in Sections 4, 5.4, 5.5 and 5.6.5 to enhance clarity and consistency with Appendix 6.5.
3. The cut-off for the of FACE-Q Satisfaction with Skin as one of the definitions for Fitzpatrick Safety Cohort was changed from 39 for the overall raw score to 69 for the overall converted score in Table 4-1.
4. The definition of “baseline” for the effectiveness and safety variables in Section 5.1 was changed to “the last non-missing assessment prior to the latter of randomization or first treatment in the control period” due to possibility of participants who were mis-treated (ie., either randomized to Volite but was not treated or randomized to Control but received Volite)
5. The multiple imputation for the primary effectiveness analysis described in Section 5.3.2 was revised to (1) include the baseline ACSS score and age in the model based on the correlation with the primary endpoint to be imputed (ie., ACSS score at Month 1 of CP) and (2) number of imputed dataset is increased from 5 to 30 to reduce variability and increase the efficiency of estimates
6. The derivation for skin hydration and analyses of following variables were added to other effectiveness analyses in Section 5.5:
 - a. raw value and change from baseline in ACSS
 - b. raw value and change from baseline in AFLS
 - c. item scores and aggregated categories for FACE-Q Satisfaction with Skin
 - d. item scores and aggregated categories for FACE-Q Appraisal of Lines
7. The analysis of ISR in Section 5.6.3 was revised to include: (1) ISR by maximum severity for summaries up to 30 days and beyond 30 days after treatment, (2) analysis of “other symptoms” based on the coded terms assigned by the Medical Safety Physician

JUVÉDERM VOLITE™ XC

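### Neither the ACSS nor the AFLS responder comparison adjusts for baseline severity, a two-level factor already collected; stratifying would bring a modest gain whose size the documents do not fix

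*Protocol*

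**What the plan says.** **Baseline levels.** Protocol 6.1, criterion 2, for the main cohort: "Has an ACSS score of 2 for both cheeks or 3 for both cheeks on the 5-point Allergan Cheek Smoothness photonumeric scale". The Fitzpatrick V/VI safety cohort may enter with other scores, but SAP Table 4-1 excludes it from the mITT population, which also requires a baseline ACSS on both cheeks. AFLS is not an entry criterion. SAP Section 3 allows for up to 75 of 210 subjects outside 2/2 or 3/3, and SAP 5.4.2 makes the comparison "using the mITT population with baseline AFLS score of 2 on both cheeks or 3 on both cheeks".

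**Comparisons.** Protocol 10.3.1.2: "A 2-sided, Fisher's exact test at the 5% level will be used to test whether the ACSS responder rate at Month 1" differs between the arms. SAP 5.3.2 replaces this with a risk difference from each of 30 imputed datasets, pooled with a normal approximation. The code line is "tables trt01p*resp/riskdiff", with no stratum. SAP 5.4.2 uses an unstratified Fisher's exact test for AFLS.

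**Where baseline severity is used.** SAP Appendix 2, item 5, revises the imputation model to "include the baseline ACSS score and age in the model based on the correlation with the primary endpoint to be imputed". SAP 5.7.1 lists the subgroup "Baseline ACSS score: 2 and 3". SAP Table 5-4 summarizes raw ACSS and AFLS values by arm. Neither sensitivity analysis in SAP 5.3.3 adjusts for baseline.

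**Randomization.** It is within site (Protocol 7.4), and Protocol Appendix 6 lists no stratification factor. Severity is balanced only by chance.

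**The concern.** A factor with two levels, recorded for essentially every analysed subject, is the easiest kind to adjust for. If the chance of a 1-point improvement differs between subjects who start at 2 and those who start at 3, the crude comparison carries variance that a stratified one removes. It also lets a chance imbalance in severity pass straight into the estimated difference.

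The existing uses of baseline ACSS do not deal with this. The imputation model touches only missing values, the subgroup rates are reported separately, and the summaries would show an imbalance without correcting for it. If an imbalance appeared, an adjustment chosen after unblinding would be open to challenge. At stake are the width of the primary confidence interval and some power for AFLS.

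**Working it through.** **Inputs from SAP Section 3.** ACSS: 112 versus 56, 80% versus 40%, 2-sided 5% ("A sample size of 112 participants in the treatment group and 56 participants in the control group will provide 99.9% power"; "The treatment group is assumed to have at least an 80% responder rate at Month 1"). AFLS: 72 versus 36, 80% versus 45%, stated power 94.4%.

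**Assumptions, not in the documents.** The responder-rate gap *d* between baseline 2 and 3 is 0 to 40 points and equal in both arms. The share *f* in one stratum is 50%, with 30% also checked. A 40-point gap is the ceiling for this split: it puts the VOLITE strata at 100% and 60%.

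**Step 1: the plan's own figures.** Enumerating both binomials with 2-sided Fisher p < 0.05 gives 99.91% for ACSS (stated 99.9%) and 94.40% for AFLS (stated 94.4%). Both reproduce.

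**Step 2: variance.**
- Crude: V = p1(1−p1)/n1 + p0(1−p0)/n0
- Removed by stratifying: f(1−f)d² × (1/n1 + 1/n0)

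ACSS crude: 0.16/112 + 0.24/56 = 0.005714, SE 0.0756, 95% half-width 14.8 points. At d = 0.2: 0.25 × 0.04 × (1/112 + 1/56) = 0.000268, which is 4.7% of the crude variance.

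AFLS crude: 0.16/72 + 0.2475/36 = 0.009097, SE 0.0954, half-width 18.7 points. At d = 0.2: 0.01 × (1/72 + 1/36) = 0.000417, which is 4.6%.

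**Step 3: AFLS power.** 40,000 simulated trials per gap (simulation error about 0.1 points) compared Fisher, unstratified chi-square and Cochran-Mantel-Haenszel (CMH) stratified by baseline.

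| Gap (points) | ACSS variance reduction | ACSS half-width | AFLS variance reduction | AFLS half-width | AFLS Fisher | AFLS chi-square | AFLS CMH |
|---|---|---|---|---|---|---|---|
| 0 | 0% | 14.8 | 0% | 18.7 | 94.34% | 95.83% | 95.59% |
| 10 | 1.2% | 14.7 | 1.1% | 18.6 | 94.55% | 95.82% | 95.85% |
| 20 | 4.7% | 14.5 | 4.6% | 18.3 | 94.43% | 95.75% | 96.51% |
| 30 | 10.5% | 14.0 | 10.3% | 17.7 | 94.42% | 95.79% | 97.33% |
| 40 | 18.8% | 13.4 | 18.3% | 16.9 | 94.32% | 95.77% | 98.45% |

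Over the same gaps, ACSS power under CMH is 99.93 to 100.00%, so there is nothing material to gain in the test. With 30% in one stratum, the 20-point reductions fall to 3.9% (ACSS) and 3.8% (AFLS).

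**Step 4: where the AFLS gain comes from at 20 points.** Fisher to unstratified chi-square: 95.75 − 94.43 = 1.32 points. Chi-square to CMH: 96.51 − 95.75 = 0.76 points, or about 0.7 against the rounded 95.8%. Only the second part is due to baseline. With a common AFLS rate of 45%, type I error is about 3.9% for Fisher, 4.7% for chi-square and 4.9% for CMH, so the stratified test holds its level.

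**Step 5: chance imbalance.** The SD of the between-arm difference in severity share is √(0.25/112 + 0.25/56) = 8.2 points for ACSS and √(0.25/72 + 0.25/36) = 10.2 points for AFLS. At a 20-point gap, a 1-SD imbalance moves the crude difference by 0.2 × 8.2 = 1.6 points and 0.2 × 10.2 = 2.0 points. This is the variance of Step 2 seen another way (0.016² ≈ 0.00027), not a second gain on top of it.

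**The case against.** The strongest objection is that the documents do not show that baseline 2 versus 3 predicts response. A reader might infer from Appendix 2, item 5, that the sponsor has already said so. It has not: that item concerns correlation with the Month 1 score. A starting score can correlate with a later score while the chance of a 1-point drop is the same at both levels. Listing a subgroup is not evidence either. The V12-001 figures in Protocol 3.2 pool moderate with severe, and their contrast with all treated subjects changes direction: 96.2% overall versus 89.4% in moderate or severe cheeks at Month 1, but 34.9% versus 40.5% at Month 6. This stands. The gain is conditional, and with no gap it is zero.

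Three other stronger readings also fail.
- That every effectiveness subject enters at 2/2 or 3/3 on both scales: true of ACSS apart from eligibility errors, but for AFLS it is only a restriction of the analysis subset.
- That baseline severity is ignored altogether: it is in the imputation model, the summaries and the ACSS subgroup.
- That AFLS power would rise from 94.4% to 96.5% because of baseline: most of that rise comes from leaving Fisher's test.

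There are practical objections too. The unadjusted test is valid, and its type I error already allows for chance imbalance. Protocol 10.3.1.3 has AFLS analysed like ACSS, that is by Fisher's test, so CMH would be a new departure; the SAP has, however, already made such a departure for the primary endpoint. A subject randomized in error with another ACSS score, outside the safety cohort, stays in mITT and fits neither stratum. Simple within-stratum variances can collapse: with a 95% rate in one VOLITE stratum, the chance of no non-responders is 0.95^36 = 16% for AFLS and 0.95^56 = 6% for ACSS. These points shape the fix but do not remove the case for it.

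**Conclusion.** The point holds as a low-cost refinement with a modest gain. Both responder comparisons are unadjusted for baseline severity, randomization does not balance it, and no planned sensitivity analysis adjusts for it.

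The size rests on an assumed responder gap. With equal strata, gaps of 10 to 20 points are worth about 1 to 5% of the variance on either scale. Only the extreme 40-point case reaches 18 to 19%. For ACSS the benefit is a slightly narrower interval and protection from chance imbalance. A reader might infer that the primary conclusion is in danger, but at 99.9% stated power it is not. For AFLS, baseline itself adds about 0.7 power points at a 20-point gap. If severity is not prognostic, stratifying loses about 0.2 points against an unstratified chi-square.

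**What to change.** Amend the SAP before the randomization schedule is released.

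- **5.3.2:** in each imputed dataset, estimate a Mantel-Haenszel or size-weighted risk difference stratified by baseline ACSS (2/2 versus 3/3), and pool as now. With stratum-size weights the target stays the overall risk difference.
- **5.4.2:** compare AFLS responders with a test and risk difference stratified by baseline AFLS (2/2 versus 3/3). Use CMH, or an exact stratified test to stay closer to the protocol's Fisher test.
- State which stratum takes any mITT subject whose baseline ACSS is neither 2/2 nor 3/3.
- Name a variance estimator that tolerates zero cells.
- Keep the crude analyses as supportive.

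The cost is SAP wording, a few lines of code and a documented departure from the protocol's Fisher test for AFLS. No new data are needed.
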